#### III. Data Collection

Patient data will be collected based on chart review, observations, actigraphy, and staff proxy informant interviews. Family CG data will be collected via electronic surveys on a tablet or by paper if a participant chooses. At all measurement time points, research evaluators will end data collection with the patient if he/she observes signs of dissent from the patient which includes: verbal refusal to answer a question, closing eyes and refusing to respond, asking the evaluator to leave, and moving away from the evaluator. The training of evaluators will include interrater reliability (minimum of 90%). Evaluators will not be informed of randomization results or provided with the details of the intervention. The research evaluators are fluent in Spanish and will use translated consents and study materials, in the event that Spanish is the primary language. The RedCap system will be used for screening of participants and data collection. The same data is collected on the intervention and control units. Descriptive (one-time) and outcome (multiple time-points) data are collected.

*Upon enrollment, within 48 hours of admission to the unit, patient and family CG descriptive measures* will be collected. Patient characteristics will include age, race/ethnicity, gender, marital status, education, medical diagnoses, medications, the use of sensory and mobility devices, and disease burden. Comorbid conditions will be classified with the *Charlson Comorbidity Index*.  Pre-admission function (ADL performance 2 weeks prior to admission) using the *Barthel Index*  (also an outcome measure) will be evaluated based on report from the family CG. Evaluation of hearing loss will be assessed using The Whisper Test. Pain will be measured using the Pain Assessment in Advanced Dementia and The Verbal Descriptor Scale. Upon discharge, length of stay, use of tethers (IV lines, pulse oximetry, urinary catheters, etc.), physical restraint use, and discharge disposition will be acquired. Cognitive *domains affected* by both dementia and delirium will be evaluated: executive function, orientation, memory, abstract thinking, and attention, evaluated by the subdomains of the *MoCA*.  The types of interventions provided on the FamPath assessment and care plan will be collected for descriptive purposes, extracted at the completion of the intervention.

We would like to test the efficiency of a new app to detect delirium and validate its use. The content includes 2 new questions (Ultra-brief CAM); the other questions are ones that we currently ask in the MoCA and CAM-Severity scale. We will test the app upon enrollment and each day until discharge. Thus, we will be extending our data collection time to less than one minute.

Here is the following description of the App: The READI delirium assessment app uses the REDCap application programming interface (API) for use on the iPad Air® tablet. The app executes the adaptive testing of the 2-step protocols using the Ultra-brief CAM and the 3D-CAM and together they take less than one minute to administer. The app allows the user to record accuracy of patient responses and automatically times each question. A pause button is available for interruptions. On subsequent days, the app retrieves information from the previous day's assessment to automatically assess for acute change. At the end of the assessment, the app reports the presence or absence of delirium, and uploads data into RedCAP, a HIPAA-compliant secure research database.

Family CG descriptive measures will include age, race, gender, marital status, education, relation to patient, employment status, other caregiving responsibilities, number of additional caregivers, and health literacy. General health and change in health compared to one year ago will be assessed using two widely used items from the SF-36. Health Literacy (reading) will be measured with the *REALM-short form*). The *REALM-short form is highly correlated with* three other tests with a reported test-retest of 0.99. Handley will be evaluated with the seven-item Hospital Anxiety and Depression Scale (HADS) subscale for Anxiety (HADS-A) and depression with the seven-item Hospital Anxiety and Depression Scale (HADS) subscale for Depression (HADS-D). Subscale ideation will be assessed using the Ask Suicide-Screening Questions (https://www.nimh.nih.gov/news/science-news/ask-suicide-screening-questions-asq.shtml) The type and level of caregivers' participation in hospital care will be measured by the researcher-developed tool that provides a self-report of the type of care and the number of hours per week spent providing care both in the hospital and post-discharge setting. Sp,60

The use of rehabilitation therapies and psychotropic medication prescribed during the hospitalization (drug, dose, frequency of antipsychotics, antidepressants, anxiolytics, sedatives/ hypnotics, mood stabilizers), length of stay, discharge disposition, setting and contact information, will be obtained through chart abstraction **at discharge**.

The following outcome measure data collection/ will be initiated within 48 hours of admission to the unit (T0), within 72 hours of discharge (T1), and 2 month (T2) and 6 month post-discharge (T3), by research evaluators via observation, input from staff, chart abstracting or interview of the patient/family CG. Post-discharge data collection allows a one-week window post 72 hours of discharge. Also, a two-week window pre and post 2 month and 6 month time points to promote feasible and complete data collection.

The change in study procedure is due to COVID-19. The following outcome measure data collection/ will be initiated within 48 hours of admission to the unit (T0), within 72 hours of discharge (T1), and 2 month (T2) and 6 month post-discharge (T3), by research evaluators via observation, input from staff, chart abstracting or interview of the patient/family CG. Outcome measures (and additional COVID-19 questions) collected at 72 hours of discharge, 2 month and 6 month post-discharge will be completed with family CG via telephone or zoom as able. Functional performance and physical activity (objective measure) will not be collected in post-acute setting. Post-discharge data collection allows a one-week window post 72 hours of discharge. Also, a two-week window pre and post 2 month and 6 month time points to promote feasible and complete data collection.

Patient outcome measures- collected for both control and intervention group.			
Aim 1: Validate the efficacy of Fam-FFC on physical function (ADLs/ performance and physical activity), delirium occurrence and severity, behavior, mood, and adverse events.			
Measure	Tool	Description	
		Function	
ADLs (activities of daily living)	Barthel Index: verbal report of function will be obtained from the nurse who is assigned to the patient's care on the day of data collectionReturn to baseline function (ADL function 2 weeks prior to admission) will be calculated	A 14-item measure of physical function that assesses ability for self-care. 134There is sufficient evidence for the reliability and validity of the Barthel Index when used with older adults, 134, 140 individuals with progressive neurological conditions, 141 and when proxy respondents were utilized to report the functional abilities of dementia patients. 142	
Functional performance	Timed Chair Rise (observation)	An item on the Balance subscale of the Tinetti Gait and Balance Scale. 143 Previous work has identified this measure as a reliable and valid indication of function and strength. 140	
Physical activity	Objectively measured (actigraphy) for 24 hours using the Motionwatch.	The MotionWatch offers wrist-worn actigraphy that records activity in set epochs of time. 145 with established reliability and validity; 145-148 well-tolerated by cognitively impaired older adults. 148 The MotionWatch is applied within 24 hours of consent, and then upon subsequent data collection points.	
	Delir		
Delirium occurrence	Structured interview consisting of questions from the MoCA observation  and the Confusion Assessment Method (CAM). 	The CAM has high sensitivity and specificity;  validated in persons with dementia.  Delirium occurrence will be evaluated as the presence of full or subsyndromal delirium, a binary outcome (present or absent). 	
Delirium severity	Confusion Assessment Method (CAM)  149	An additive score for six items of the CAM (inattention, disorganized thinking, disorientation, memory impairment, perceptual disturbances, and psychomotor agitation/ retardation), scored as "absent" (0 points), present in mild form (1 point), or present in severe form (2 points). The seventh item, altered level of consciousness, will be scored as alert (0 points), vigilant or lethargic (1 point), and stupor or coma (2 points). Scores range 0 - 14, with a higher score indicating greater severity of delirium. 153	
	Mo	ood and Behavior	
Depression	Cornell Scale for Depression in Dementia (CSDD) 	A 19-item survey designed to assess depressive symptoms in individuals with dementia. 154, 155 There is sufficient evidence of reliability and validity. 155	
NPS	Brief Neuropsychiatric Inventory (NPI-Q) 	A 12-item, reliable, validated informant-based assessment of neuropsychiatric symptoms and associated caregiver distress. 156	

Adverse Events	Report of falls, hospitalizations,	A monthly check of the patient hospital record to evaluate for
	transfers to the emergency	hospitalizations/ED visits (in addition to the family caregiver
	department	report at month 2 and month 6).

The following outcome measure data collection will be initiated within 72 hours of discharge (T1), and 2 month (T2) and 6 month post-discharge (T3), by research evaluators via interview of the patient/family CG

Family Caregiver Outcome Measures- collected for both control and intervention group.			
Aim 2: Evaluate the imp	Aim 2: Evaluate the impact of Fam-FFC on Family CG-centered outcomes.		
	All measures are self-rated and will be initiated within: 72 hours of discharge (T1), 2 (T2) and 6 months post-discharge (T3). This data is collected via pen/paper tools completed by family CG.		
Measure	Measure Tool Description		
Preparedness for caregiving	Preparedness for Caregiving Scale 	An 8-item instrument that asks caregivers how well prepared they believe they are for multiple domains of caregiving: physical care and emotional support, setting up support services, dealing with the stress of caregiving. Items are rated 0 (not at all prepared) to 4 (very well prepared); shows very good reliability and internal consistency, 157 including in family CGs of hospitalized persons with dementia. 59	
Caregiver Strain	Modified Caregiver Strain Index (CSI) 	A 13-question tool that measures strain (financial, physical, social, psychological, and personal) related to care provision, with excellent internal consistency and reliability. 158,159	
Caregiver Burden	Zarit Burden Interview (ZBI-12)  short version	12-item tool that measures caregiver perception of burden has shown high internal consistency and discriminative ability in caregivers of persons with dementia. 160,161	
Desire to Institutionalize	Desire to Institutionalize Scale 	6-item scale with moderate reliability; Cronbach alpha = 0.694.162	

**Nurse Champion Interviews**: For the exploratory aim of assessing the cultural appropriateness of the intervention, the six nurse champions (intervention units) will be consented and interviewed, using a semi-structured interview guide, after the study ends in his/her particular unit/setting to provide their perspective. Qualitative content analysis of audiotaped, transcribed interviews will be conducted. The research evaluators will be trained to conduct these interviews.

**Staff Nurse Interviews**: Staff nurses will also be recruited at the end of the intervention at each study site, to participate in a focus group to determine their views on the effectiveness and sustainability of the intervention. We anticipate having 6-8 nurses per site (representing all three intervention units). This number is based upon our past experience recruiting for focus groups in this type setting, and the expected number to reach data saturation. However, if more than nurses volunteer/ want to participate, and/or the responses indicate the need to elicit more participation, we will add focus groups at the site. The PI and a member of the research team will conduct these interviews.

Family CG interviews: For the exploratory aim of assessing the cultural appropriateness of the intervention, we will recruit *family CGs* who self-identify as black, Latino, Asian and white, randomly selected from the Fam-FFC (intervention) sample. Approximately 10 percent of families from each ethnic group represented in the study will be approached for consent for participation in these interviews. Qualitative content analysis of audiotaped, transcribed interviews will be conducted at the six-month post-hospital discharge visit. A draft semi-structured interview guide will be refined with the input of a hospital patient /family council. Additional COVID-19 questions be asked during interview of the family CG. The research evaluators will be trained to conduct these interviews.

Cost Outcomes Aim3: Evaluate the relative costs for Fam-FFC v. control condition; calculate health care cost (post-acute health care utilization) and total cost savings for Fam-FFC. We have developed cost-related data collection forms, specifically Activity Diaries, to help facilitate data collection for the champions, research nurse facilitators, and staff. These include staff and research nurse time and hours worked, training time (including replacement), supplies, and incentives. Post—acute utilization will be evaluated with a cumulative count of emergency room visits, number/days of hospitalizations, and long-term nursing home admissions six months after discharge, obtained from questioning of the family at each point of data collection. Health care unit charges and reimbursement rates will be obtained from yearly publications from the American Hospital Associations and other health data organizations.

Treatment Fidelity. Treatment fidelity will be evaluated with regard to delivery of the intervention, receipt, and

enactment as shown in Table 5. Assessment of Environment and Policy will be conducted by the Fam-FFC Research Nurse with champions as part of the intervention (See Component 1). Knowledge of Fam-FFC is a valid and reliable 15-item paper and pencil multiple choice exam that tests staff knowledge about Fam-FFC. The Goal Attainment Scale  evaluates attainment of up to four patient goals and will be completed by the Fam-FFC Research Nurse with input from CGs, champions, nursing staff, and other health care professionals who work with the patient. This will be reviewed at discharge and post-discharge data collection points. The FamPath Audit tracks delivery of FamPath and Family CG Activity Logs monitor CG involvement and agreement with the care plan. The Function Focused Care Behavior Checklist (FFC-BC) is a valid and reliable objective measure including a 19-item checklist reflecting nursing staff performance of Fam- FFC. Oversight of treatment fidelity will be provided by the co-investigator (BR) who will collaborate with the research team to ensure adherence to the study manual of operations and standardization across sites. See below for a comparison of treatment fidelity for treatment and control sites.

Treatment Fidelity (Bolded items: both treatment and control sites; items not bolded: treatment site only)		
Focus	Data (Appendix B)	Evidence of Treatment Fidelity
Delivery	Environment/Policy Assessments 59,60 (Component I)	Completion of assessments by Fam-FFC Research Nurse
	Education: Percentage of nurses exposed (Component II)	80% of all nursing staff working on participating nursing units (# exposed/total # nursing staff)
	Goal Attainment Forms  (Comp. III)	Forms completed on all recruited patients in treatment units
	Fam-Path Audit (Component IV) 59,60	Completion of: bedside goals and treatment plans, discharge checklist, post-acute follow-up and plan update, communication with post-acute provider
Receipt	Knowledge of Fam-FFC Test 59, 60	Mean score of > 80% among nursing staff after Education
	Environment/Policy Assessments 59, 60	Evidence of change(s) made over the course of the study
	Goal Attainment Scale 119	Positive goal attainment scores incorporated into care plans
Enactment	FFC Behavior Checklist 59, 60, 120	Performance of Fam-FFC by nurses based on observations of care interactions in the hospital
	Family CG Activity Logs 59,60	Family CG involvement in care and follow-through on plan.

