## 7.0 Study Design and Procedures

#### 7.1 Study Design

Describe the type/design of trial to be conducted (e.g., double-blind, placebo controlled, parallel design, etc.). Provide a schematic diagram of study design, procedures and stages, if appropriate.

The experimental design for this study is a repeated measures analysis with study units randomized by clustering to either treatment (Fam-FFC) or the control condition. This allows a within- and betweengroups analysis to ascertain the effects of Fam-FFC.

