#### 8.3 Statistical methods

Describe the statistical methods (or non-statistical methods of analysis) that will be employed.

Aim 1: Validate the efficacy of Fam-FFC on physical function (ADLs/ performance and physical activity), delirium occurrence and severity, behavior, and mood. For each outcome, an appropriate mixed effects model (either a LME or a GLMM) will be identified for model fitting. For delirium occurrence (a binary variable) we will use generalized linear mixed models with a logistic link function. The primary independent variables will be GROUP (Fam FCC v. control), TIME (day of admission, day of discharge, 2-month post discharge and 6-month post discharge) and SITE (for the three hospitals). The TIME x GROUP interaction will be tested for differential rate of change in the outcome. The GROUP x SITE interaction will be tested for heterogeneous center effects. Three-level models using an unstructured correlation will be fitted for the repeated measures within individuals who are nested within the same inpatient unit. 181-184 Time will be modeled continuously using day since admission so that trajectories can vary across individuals depending on time spent in the inpatient unit. This also allows us to examine non-linear time functions (e.g., quadratic) that allow the rate of change to vary over the different intervals. Covariates identified from the baseline analyses will be included in the mixed model to adjust for their influences. We will also consider interactive effects among demographic variables of interest (e.g., age, gender of patient and caregiver, ethnicity) and treatment condition to identify moderators of the treatment effects. Bootstrap methods will be applied to the mixed effects models in addition to the Wald test and the likelihood ratio test within the mixed effects models. 185-187 Subject level propensity score matching will be applied to improve the statistical power of the planned hypothesis tests.  To address the multiple endpoints issue in this trial, P<0.05 for the primary hypothesis and then multiple testing procedures such as closed testing implemented in PROC MULTTEST will be applied to adjust p values. 188-190

Aim 2: Evaluate the impact of Fam-FFC on family CG-centered outcomes (family CG preparedness for caregiving, strain, burden, and desire to institutionalize). LME similar to Aim 1, will be used.

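### For the caregiver hypothesis (H3), the only treatment-over-time test stated is a slope among post-exposure visits; no level contrast is named as the test

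*Combined protocol and SAP*

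**What the plan says.** H3 (Section 1.1) states that caregivers in the Fam-FFC arm will do better than controls on preparedness, strain, burden and desire to institutionalize. It names no visit and no rate of change. Section 1.2 lists these outcomes among the primary endpoints.

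The schedule for the four scales is in Section 7.2, Family Caregiver Outcome Measures: "All measures are self-rated and will be initiated within: 72 hours of discharge (T1), 2 (T2) and 6 months post-discharge (T3". Caregiver data taken at enrolment are descriptive (demographics, health, literacy, HADS, suicide screen, participation in care) and include none of the four scales. The intervention starts in hospital (Sections 7.2 and 7.4.2), so T1 is already post-exposure.

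The Aim 2 analysis in Section 8.3 is one sentence: "LME similar to Aim 1, will be used". The Aim 1 model lists GROUP, TIME and SITE as its main variables. Its stated treatment-over-time test is: "The TIME x GROUP interaction will be tested for differential rate of change in the outcome". TIME is described first by occasion, "TIME (day of admission, day of discharge, 2-month post discharge and 6-month post discharge) and SITE (for the three hospitals", and then by day: "Time will be modeled continuously using day since admission so that trajectories can vary across individuals". Section 7.1 says of the design: "This allows a within- and betweengroups analysis to ascertain the effects of Fam-FFC".

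**The concern.** The Aim 1 model suits outcomes with an admission value, where a treatment effect appears as divergence from a common start. The caregiver scales have no such start. Any benefit gained in hospital is already in the T1 score, and TIME x GROUP sees only what happens to the difference afterwards.

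An analyst who follows the stated test could therefore report no effect when every visit favours Fam-FFC equally, or a worse trajectory when a real benefit fades. An analyst who uses GROUP instead has a term whose meaning depends on how TIME is coded, and Section 8.3 gives two codings. One of them includes an admission occasion that does not exist for these outcomes. The choice could be made after the data are seen.

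Section 8.3 also says that "multiple testing procedures such as closed testing implemented in PROC MULTTEST will be applied to adjust p values". Such a procedure needs one p-value per hypothesis, and the plan does not say which p-value H3 supplies.

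**Working it through.** **Step 1. The plan's own figure.** The target of 438 is consistent: 73 x 6 = 438 and 146 x 3 = 438. The 80% power claim in Section 8.2 cannot be reproduced, because no effect size, SD or ICC is given. This point does not depend on it.

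**Step 2. A result that needs no assumptions.** Let d1, d2, d3 be the between-arm differences at T1, T2, T3. Any TIME x GROUP term is built from contrasts among these three. If d1 = d2 = d3, it is zero whether TIME is linear, quadratic or categorical. Two-sided rejection is then 5% at any sample size, 2.5% in each direction.

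**Step 3. Inputs for the illustrations.** From the documents: 438 dyads, 20% attrition, six units (three per arm), alpha 0.05. Assumed: two-sided testing; visits at days 6, 66 and 186; within-person correlation rho 0.3-0.7 (compound symmetry); unit ICC 0.02, constant over visits; the effect patterns below, in SD units. Completers per unit: 438 x 0.8 / 6 = 58.4.

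**Step 4. Estimates.** The mean day is 86, the deviations are -80, -20 and 100, and their sum of squares is 6,400 + 400 + 10,000 = 16,800. Under these assumptions the interaction slope is sum(deviation x d) / 16,800, and the GROUP coefficient at day 0 is mean(d) - 86 x slope.

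- Fading (0.5, 0.4, 0.25): slope = (-40 - 8 + 25) / 16,800 = -0.00137 per day, or -0.246 SD over 180 days. Day-0 GROUP = 0.3833 + 0.1177 = 0.501.
- Growing (0.25, 0.4, 0.5): slope = (-20 - 8 + 50) / 16,800 = 0.00131. Day-0 GROUP = 0.271.
- Late (0, 0.3, 0.6): slope = (0 - 6 + 60) / 16,800 = 0.00321. Day-0 GROUP = 0.024.
- Constant 0.5: slope = 0. Day-0 GROUP = 0.500.

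Day-0 GROUP is therefore close to the T1 difference in all four patterns. Moving T1 to day 4, 10 or 17 changes the late-pattern value only to 0.030, 0.011 or -0.012.

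**Step 5. Power.** The covariance matrix of the three differences is V = (2/3)[ICC x J + (R - ICC x J)/58.4], where R is the within-person correlation matrix and J is all ones. For the T1-T3 average the variance is (2/3)[ICC + ((1 + 2 rho)/3 - ICC)/58.4]. At rho 0.5 this is (2/3)(0.02 + 0.01107) = 0.0207, so SE = 0.144, and 0.5/0.144 = 3.47 gives 73.9% power (noncentral t, 4 df). Ranges below cover rho 0.3-0.7. Figures are power in favour of Fam-FFC, except that the joint test of GROUP and TIME x GROUP (F on 2 and 4 df) is non-directional.

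| Pattern | Day-0 GROUP | TIME x GROUP | T1-T3 average | Joint test |
|---|---|---|---|---|
| Constant 0.5 | 68-70% | 2.5% | 71-77% | 51-57% |
| Fading | 68-70% | 0% (33-63% significant against) | 50-55% | 53-66% |
| Growing | 27-28% | 31-59% | 50-55% | 52-63% |
| Late | 3% | 93-99.9% | 34-38% | 86-99% |

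**Step 6. Sensitivity of the average contrast.** If SITE is a fixed effect, 6 units - 3 sites - 1 group leaves 2 df, and the four rows become 45-50%, 31-35%, 31-35% and 22-24%. For a constant 0.5 SD at ICC 0.01, 0.02 and 0.05, power is 84-91%, 71-77% and 46-49% on 4 df, and 56-64%, 45-50% and 29-31% on 2 df. For a constant 0.3 SD at ICC 0.02 it is 34-38% on 4 df and 22-24% on 2 df. No multiplicity adjustment is included.

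**The case against.** The strongest reply is that nothing is untestable. GROUP is a listed primary variable, the design section foresees a between-groups comparison, and day-0 GROUP has 68-70% power for the very benefit that TIME x GROUP misses. This stands. A reader might infer that the plan or its data cannot answer H3; the documents do not support that. What is missing is the designation of a test.

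A reader might also infer that the day-0 GROUP coefficient is misleading. It is not: it tracks the T1 difference in every pattern, and a value near zero is correct when the T1 difference is zero. It simply says little about T2 and T3.

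Section 8.3 also mentions Wald and likelihood ratio tests. A joint test of GROUP and TIME x GROUP would have 51-99% power across the four patterns, so the fitted model is not blind to any of them. That is fair, but the joint test gives no direction and the plan does not name it for H3.

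Nor is the T1-T3 average best everywhere. It loses to day-0 GROUP for the fading pattern and to TIME x GROUP for the late one. It is one defensible level contrast.

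Finally, Aim 2 says similar, not identical, and the stated reason for counting days is variation in hospital stay, which matters less for outcomes measured after discharge. TIME by visit is therefore a permissible reading. It leaves Step 2 unchanged, because a constant difference gives zero interaction under either coding.

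**Conclusion.** The point holds in this form. For the caregiver scales, the one treatment-over-time test that Section 8.3 states is a comparison of slopes after exposure. It has expected value zero for an early, maintained benefit and the wrong sign for a fading one, while H3 is a between-arm difference. No level contrast is designated in its place. The zero-interaction result is exact.

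All power figures are illustrations on assumed effects, ICC, correlation and visit days. They use compound symmetry although the plan specifies an unstructured correlation, 438 dyads although Section 8.1 now expects 458-468, and 20% loss at every visit. They also give the slope only 4 df. If the unit effect is constant over visits it could have more, which would raise both its wrong-direction risk under fading and its power for late effects.

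This should be fixed before analysis. The data can answer H3; the written plan does not say how.

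**What to change.** In a dated SAP amendment, made before anyone sees outcomes by arm:

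- For Aim 2, code TIME as visit (T1, T2, T3).
- Name one level contrast as the H3 test. The GROUP difference averaged over T1-T3 is a reasonable default; the difference at one stated visit would also serve. Make TIME x GROUP secondary.
- Section 8.3 already provides that "Covariates identified from the baseline analyses will be included in the mixed model to adjust for their influences". Name the covariates for Aim 2 from data already collected near admission: caregiver HADS-A and HADS-D, T0 NPI-Q caregiver distress, and the pre-admission Barthel Index.
- State whether SITE is a fixed effect (2 df) or not (4 df), and report the clustered power of the chosen contrast.

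No new visit or measure is needed. Section 8.2 indicates that recruitment has reached the last site, so the amendment is time-sensitive.

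The cost should be stated openly. Without a baseline score the level contrast relies on balance between six units, its clustered power is modest, and it has less power than a slope test for an effect that builds late, which the post-discharge calls make plausible.

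### Research evaluators who are meant to be masked are assigned the intervention-only caregiver interviews at six months, so any evaluator who conducts one learns the arm of both units at that hospital

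*Combined protocol and SAP*

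**What the plan says.** Section 7.2, part III sets the masking rule: "Evaluators will not be informed of randomization results or provided with the details of the intervention". This is the only statement on evaluator masking. Section 7.4.5 (Blinding of the Test Article) covers only participants, and only before consent.

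The same part gives evaluators the outcome work. Patient outcomes run from T0 through "6 month post-discharge (T3), by research evaluators via observation, input from staff, chart abstracting or interview of the patient/family CG", and caregiver outcomes from T1 to T3 are collected "by research evaluators via interview of the patient/family CG". Sections 4.4 and 7.2 (part I) also have the research evaluator check caregiver eligibility and screen patients with the MoCA, AD8, CDR and FAQ.

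Later in part III, caregivers "randomly selected from the Fam-FFC (intervention) sample" are to be interviewed about the cultural appropriateness of the intervention. The fraction is "Approximately 10 percent of families from each ethnic group represented in the study". On timing the text reads "interviews will be conducted at the six-month post-hospital discharge visit". Strictly, the subject of that sentence is the content analysis, but the table in section 8.3 places the interviews themselves at the six-month contact. The paragraph ends: "The research evaluators will be trained to conduct these interviews". The same sentence closes the paragraph on nurse champion interviews. The staff-nurse focus groups are assigned differently: "The PI and a member of the research team will conduct these interviews".

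Section 16.5 instead mentions a single study nurse evaluator who is trained for the qualitative interviews. Section 7.4.3 randomises units within each hospital, one to Fam-FFC and one to control. I read its reference to six hospitals as six units in three hospitals, as in sections 4.2 and 16.1.

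**The concern.** The plan promises to withhold two things from evaluators: the arm and the content of the intervention. A qualitative interview with an intervention caregiver about Fam-FFC discloses both. Because allocation is by unit, the disclosure is not confined to one family. The interviewer knows which unit the patient came from, so that unit's arm is revealed and the other unit's follows by elimination.

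The interviews also start early relative to the site's timeline. The first six-month contacts fall while that hospital is still enrolling, so an unmasked evaluator could go on to screen new dyads and rate outcomes on units whose arm is known. In a trial whose participants and nursing staff are not masked after enrolment, that is a loss worth avoiding.

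**Working it through.** **Step 1. Set the provisions side by side.**

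- Masked role: research evaluators (7.2 III).
- Role collecting outcomes from T0 to T3 and screening dyads: research evaluators (7.2 I and III, 4.4).
- Role conducting caregiver interviews: research evaluators (7.2 III).
- Interview sample: intervention arm only. Timing: six months, which is T3.
- No section names a separate interviewing team, bars an interviewer from outcome rating, or orders the interview after the T3 measures.

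Followed as written, the plan breaks its own masking rule. No arithmetic is needed for that.

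**Step 2. Number of interviews.** Section 8.2 gives 73 per unit. Three intervention units give 3 × 73 = 219 caregivers, and 10% is 21.9, about 22 in all or about 7 per unit. Interviewing may continue until saturation, so 22 is not a ceiling.

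**Step 3. How much could follow the first interview.** The documents give no figure, so this is illustrative.

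- From section 7.2: enrolment in months 3 to 14 (elapsed time 2 to 14), T2 and T3 at 2 and 6 months after discharge, and a two-week window either side.
- Assumed: uniform enrolment, a hospital stay of 0 to 0.5 month, the four visits weighted equally, and every evaluator at the hospital unmasked at the first interview.

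For a visit at offset *v* months after enrolment and a first interview at elapsed month *t*, the share still to come is (14 + *v* − *t*)/12, limited to the range 0 to 1. For *t* = 9.75 and offsets 0, 0.25, 2.25 and 6.25: 4.25/12 = 35%, 4.5/12 = 38%, 6.5/12 = 54%, 10.5/12 = 88%; mean 54%.

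| First interview (elapsed month) | Offsets | T0 | T1 | T2 | T3 | Mean |
|---|---|---|---|---|---|---|
| 7.5 | 0, 0, 2, 6 | 54% | 54% | 71% | 100% | 70% |
| 8.25 | 0, 0.25, 2.25, 6.25 | 48% | 50% | 67% | 100% | 66% |
| 9.75 | 0, 0.25, 2.25, 6.25 | 35% | 38% | 54% | 88% | 54% |
| 10.48 | 0, 0.5, 2.5, 6.5 | 29% | 34% | 50% | 84% | 49% |
| 11.25 | 0, 0.25, 2.25, 6.25 | 23% | 25% | 42% | 75% | 41% |

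An early first interview is likely. If 7 of 73 are drawn at random, the chance that at least one of the first *j* enrollees is sampled is 1 − C(73−*j*, 7)/C(73, 7): 41% for *j* = 5, 66% for 10 and 91% for 20.

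**Step 4. Sensitivity.**

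- Attrition: weighting T2 and T3 by 0.8 (the 20% in section 8.2), the central case becomes (0.354 + 0.375 + 0.8 × 0.542 + 0.8 × 0.875)/3.6 = 52%, little changed from 54%.
- Staffing: if only one of *m* evaluators with equal workloads does the interviews, 54% falls to 54%/*m*, so 27% for two and 18% for three. The documents do not give *m*.

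**Step 5. Champion interviews.** Section 7.2 puts them after the study ends in the unit; the table in section 8.3 puts them when the intervention concludes at the site. If the latter meant month 14, then 2/12 to 2.5/12 = 17% to 21% of T2 and 6/12 to 6.5/12 = 50% to 54% of T3 assessments would be outstanding. If all follow-up has ended, none would be.

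**The case against.** The best defence is that section 16.5 points to one study nurse evaluator for the qualitative interviews, who may be separate from the outcome evaluators. That is possible, but no section excludes that person from screening or rating, and section 7.2 names research evaluators twice. The passages need reconciling at the least.

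Several stronger readings are tempting and are not supported:

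- *Every evaluator at a hospital is unmasked.* This depends on staffing that is not described.
- *Unmasking carries to later hospitals.* Units are randomised within each hospital, so one hospital's allocation does not reveal another's. Knowledge of content could carry over only if the same evaluators move between sites, which is not stated.
- *Champion interviews are an equal breach.* Sections 3.1, 4.2 and 7.2 place them after the study ends in the unit. Only section 8.3 is looser, and if the intervention includes the follow-up calls (section 7.4.2), it ends at about T3 for each dyad.
- *All outcomes are equally exposed.* The Barthel comes from the assigned nurse or, after discharge under the COVID-19 procedure, from the caregiver. The NPI-Q is informant-based and the caregiver scales are self-rated. Under the COVID-19 procedure, chair rise and actigraphy are not collected after discharge. CAM and CSDD are the most exposed: CAM severity is graded absent, mild or severe, and the outcome table names no separate informant for the CSDD.

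It is also fair to say that evaluators may guess the arm anyway, since intervention units carry a Fam-FFC bulletin board and bedside goals. That weakens masking in practice. It does not justify scheduling a disclosure that the protocol says will not happen.

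**Conclusion.** The contradiction is real and rests on the caregiver interviews. An evaluator who conducts one learns the arm of both units at that hospital and the content of Fam-FFC, possibly with enrolment and follow-up still open. Unit-level disclosure to that evaluator is a direct inference from the one-unit-per-arm design.

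The size is uncertain. About 41% to 70% of a hospital's assessments could follow the first interview if all its evaluators were unmasked, and proportionately fewer if one person did every interview. These shares rest on uniform enrolment and assumed timing, are not protocol figures, and measure exposure, not bias. The direct risk is to evaluator-scored ratings and eligibility decisions; it is smaller for nurse-, caregiver- and self-reported measures. The plan should be changed, but this does not invalidate the trial.

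**What to change.** Amend the family caregiver interview paragraph in section 7.2 in one of two ways:

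- assign the interviews to a team member who does no screening or outcome rating at that hospital; or
- hold them only after outcome collection at that hospital has closed.

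Interviewing after that dyad's own T3 measures protects only that dyad, because the unit's other patients remain to be assessed.

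The interviewer could be the project manager, who already has identifier access under sections 9.1.1.1 and 9.1.3, or one designated Spanish-speaking team member. Section 4.1 gives the project manager a part in identifying and recruiting dyads, so that part would have to stop short of eligibility decisions at the hospital concerned. Using the principal investigator looks simple, but those same sections limit identifying information to the project manager and evaluators, and Spanish fluency is stated only for evaluators (sections 5.3.1 and 7.2). The focus-group arrangement is no ready model either: section 11.0 counts evaluators as research team members, so its wording does not exclude them.

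Align the table in section 8.3 and section 16.5 with the choice, place champion interviews after the last T3 on the unit, and state evaluator masking in section 7.4.5.

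The cost is reassignment of about 22 interviews, cover for Spanish, and an update to the access wording if the interviewer is not already covered. Deferral costs recall instead: with a stay of 0.25 month, the earliest six-month contact is near elapsed month 8.25 and the last near 14 + 6.25 = 20.25, a delay of up to about 12 months. It would also exceed the participation period in section 7.3.
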